2.1.1.1 Age ≥ 18 years

Because no dosing or adverse event data are currently available on the use of BMS-986253 as monotherapy or in combination with DNMTi in participants <18 years of age, children are excluded from this study, but will be eligible for future pediatric trials.

2.1.1.2 ECOG performance status ≤ 2 (Karnofsky $\geq 60\%$, see [Appendix A](#)).

2.1.1.3 Life expectancy greater than 6 months.

2.1.1.4 Participants must have adequate organ function as defined below:

– total bilirubin	$\leq 1.5 \times$ institutional upper limit of normal OR $\leq 3 \times$ institutional upper limit of normal in participants with Gilbert's syndrome (*except for participants with increased bilirubin levels attributed to intramedullary hemolysis, which will be allowable)
– AST(SGOT)/ALT(SGPT)	$\leq 3 \times$ institutional upper limit of normal OR $\leq 5 \times$ institutional upper limit of normal if related to disease specific cause
– creatinine clearance (by Cockcroft-Gault)	$\geq 60 \text{ mL/min}/1.73 \text{ m}^2$ for participants with creatinine levels above institutional normal.

2.1.1.5 The effects of BMS-986253 on the developing human fetus are unknown. For this reason and because DNMTi as well as other therapeutic agents used in this trial are known to be teratogenic, women of child-bearing potential (WOCBP) and men must agree to use adequate contraception (hormonal or barrier method of birth control;

abstinence) prior to study entry, for the duration of study participation, and up to 6 months after study completion and last dose of DNMTi.

2.1.1.6 Ability of subject to understand and the willingness to sign a written informed consent document.

2.1.2 Exclusion Criteria

2.1.2.1 For phase I: Participants with HR-MDS (R-IPSS ≥ 3.5) that have not yet received or received less than 2 cycles of DNMTi therapy.

2.1.2.2 Participants with LR-MDS (R-IPSS < 3.5) with the following characteristics that have not yet received or are still deriving benefit from the following standard of care therapies:

- Hgb < 10 g/dL, Epo level < 500 mU/mL: Erythropoietin-stimulating agents (ESAs)
- MDS with del5q: Lenalidomide
- MDS with ringed sideroblasts (MDS-RS) with SF3B1 mutation: Luspatercept

2.1.2.3 Participants with platelet transfusion-refractory thrombocytopenia, with inability to keep platelet threshold above 10K/mcL with transfusions or those with ongoing or uncontrolled hemorrhagic complications.

2.1.2.4 Participants with clinically significant neutropenia, ANC < 100 , with frequent hospitalizations for infection (average > 1 hospitalization per month in past 6 months)

2.1.2.5 Participants who are receiving or have received any other investigational agents within 28 days before start of study treatment.

2.1.2.6 History of allergic reactions attributed to compounds of similar chemical or biologic composition to DNMTi or other agents used in study.

2.1.2.7 Uncontrolled intercurrent illness including, but not limited to, ongoing or active infection, symptomatic congestive heart failure, unstable angina pectoris, cardiac arrhythmia, or psychiatric illness/social situations that would limit compliance with study requirements.

2.1.2.8 Pregnant women or women presently breast-feeding their children are excluded due to unknown risks to a developing fetus or infant.

2.1.2.9 Any significant disease that, in the opinion of the investigator, may impair the participant's tolerance of study treatment.

2.1.2.10 Active or uncontrolled autoimmune diseases requiring treatment.

2.1.2.11 Chronic hepatitis B or C infection, because potential immune impairment caused by these disorders may diminish the effectiveness of this immunologic therapy.

2.1.2.12 HIV-positive participants are ineligible because of the potential for decreased immune response.

2.1.2.13 Presence of any other malignancy (except basal and squamous cell carcinoma of the skin, or stable chronic cancers on hormone or targeted therapy) for which participant received systemic anticancer treatment within 24 months prior to enrollment.

2.1.2.14 Prior history of allogeneic hematopoietic stem cell transplantation.

2.1.3 Recruitment Strategies

This protocol will be advertised on NIH websites (clinicaltrials.gov, future Myeloid Malignancy Program Web Site) and on NIH social media platforms.

2.2 SCREENING EVALUATION

2.2.1 Screening activities performed prior to obtaining informed consent

Minimal risk activities that may be performed before the subject has signed a consent include the following:

- Email, written, in person or telephone communications with prospective subjects
- Review of existing medical records to include H&P, laboratory studies, etc.
- Review of existing MRI, x-ray, or CT images
- Review of existing photographs or videos
- Review of existing pathology specimens/reports from a specimen obtained for diagnostic purposes

2.2.2 Screening activities performed after a consent for screening has been signed

The following activities will be performed only after the subject has signed the consent for this study for screening. Assessments performed at outside facilities or on another NIH protocol within the timeframes listed below may be abstracted and used to determine eligibility once a participant has signed the consent for this study. Note: Given the standard nature of the planned clinical laboratories, interlaboratory variability is not a concern and participants may have clinical labs drawn locally, with results sent to the NIH study team (e.g., via fax).

Screening tests are valid for 30 days prior to enrollment unless otherwise specified.

- Medical history
- Physical examination
- Laboratory evaluations
- ECG

If protocol therapy is started > 8 days of these eligibility screening evaluations, the medical history, physical examination, laboratory evaluations, and ECG must be repeated prior to starting protocol therapy (i.e., repeated at Baseline/prior to C1D1; see Section [2.4](#)).

2.2.2.1 Histologic confirmation: All participants are required to have histologically confirmed MDS. Pathology reports from outside institutions confirming the diagnosis will be acceptable for eligibility purposes with required secondary NIH pathology review.

2.2.2.2 History and physical examination: Complete history and physical examination (including height, weight, vital signs, and performance score).

2.2.2.3 Laboratory Evaluation: Laboratory data are to be obtained:

- Hematological Profile: CBC with differential
- Biochemical Profile: total bilirubin, BUN, albumin, calcium, creatinine, SGOT [AST], SGPT[ALT], phosphorous, magnesium, potassium, sodium,

LDH, uric acid, ferritin, endogenous erythropoietin, vitamin B12, folate, copper, zinc, ANA, thyroid function studies (TSH, Free T4)

- Infectious serologies including HIV, HBV, HCV
- SARS-CoV2 testing per clinical center guidelines
- Urine and/or serum pregnancy test for female participants of childbearing potential (within 24 hours prior to start of therapy)

2.2.2.4 Cardiac Evaluation: Electrocardiogram (ECG) will be obtained.

2.2.2.5 Bone Marrow aspirate and biopsy - (May be performed during baseline evaluation) must be done within 30 days prior to treatment initiation

2.3 PARTICIPANT REGISTRATION AND STATUS UPDATE PROCEDURES

Registration and status updates (e.g., when a participant is taken off protocol therapy and when a participant is taken off-study) will take place per CCR SOP ADCR-2, CCR Participant Registration & Status Updates found at: [https://nih.sharepoint.com/sites/NCI-CCR-OCD-Communications/SitePages/OEC-Administrative---Clinical-Research-\(ADCR\).aspx?Mode=Edit](https://nih.sharepoint.com/sites/NCI-CCR-OCD-Communications/SitePages/OEC-Administrative---Clinical-Research-(ADCR).aspx?Mode=Edit).

2.3.1 Screen Failures

Screen failures are defined as participants who consent to participate in the clinical trial but are not subsequently assigned to the study intervention or entered in the study. A minimal set of screen failure information is required to ensure transparent reporting of screen failure participants, to meet the Consolidated Standards of Reporting Trials (CONSORT) publishing requirements and to respond to queries from regulatory authorities. Minimal information includes demography, screen failure reason, eligibility criteria, and any serious adverse event (SAE).

Individuals who do not meet the criteria for participation in this trial (screen failure) because of any specific inclusion/exclusion criteria by discretion of PI may be rescreened.

2.3.2 Treatment Assignment (for Phase I and II)

Cohorts in phase I:

Number	Name	Description
1	“Lower-risk” MDS: eligible lower-risk phase I participants	Participants with confirmed MDS and R-IPSS score < 3.5 (low and lower intermediate-risk) that are eligible for phase I.
2	“Higher-risk” MDS: eligible higher-risk phase I participants	Participants with confirmed MDS and R-IPSS score ≥3.5 (high and higher intermediate-risk) that are eligible for phase I.

Cohorts in Phase II:

Number	Name	Description

3	“Lower-risk” MDS	Participants with confirmed MDS and R-IPSS score < 3.5 (low and lower intermediate-risk)
4	“Higher-risk” MDS	Participants with confirmed MDS and R-IPSS score ≥3.5 (high and higher intermediate-risk)

Arms

Number	Name	Description
1	escalating doses of treatment for LR-MDS	escalating doses of BMS-986253
2	escalating dose of treatment for HR-MDS	escalating doses of BMS-986253 + DNMTi (decitabine and cedazuridine)
3	phase II dose of BMS-986253 for LR-MDS*	phase II dose of BMS-986253
4	phase II dose of BMS-986253 for HR-MD	phase II dose of BMS-986253 + DNMTi (decitabine and cedazuridine)

*Poor-risk genomic features, such as bi-allelic TP53 mutation, can escalate a participant from LR-MDS cohort #3 to HR-MDS cohort #4 for phase II, per PI discretion.

Arm Assignment

Participants in cohort 1 are assigned to arm 1; Cohort 2 assigned to arm 2; Cohort 3 are assigned to arm 3, and cohort 4 are assigned to arm 4.

2.4 BASELINE EVALUATION

To be performed within 8 days prior to initiating study treatment.

Medical Assessment:

- History and physical examination including vital signs (blood pressure, pulse, respiratory rate, oxygen saturation)
- Height and weight
- Performance status determination (see [Appendix A](#) for ECOG)
- ECG
- Concomitant medications assessment
- Questionnaires/assessments:

Note: These apply to English speaking participants only.

- Rockwood/CFS and MDS-CI Questionnaire
- European Organization for Research and Treatment of Cancer (EORTC) quality of life questionnaire = EORTC QLQC30 score
- Psychosocial Assessment

Laboratory Assessments:

- Complete blood count plus differential, platelet count, and reticulocyte count
- Serum chemistries (Na, K, Cl, CO₂, glucose, BUN, creatinine, albumin, calcium, magnesium, phosphorus, alkaline phosphatase, ALT, AST, total bilirubin, LDH, TSH, erythropoietin), CRP
- Blood type and screen (as clinically indicated)
- Urinalysis
- Research blood per section **5.1** Blood sample for T-cells, B-cells, and NK cells [TBNK] (CD3, CD4, CD8, CD19 clinical panel)
- Bone Marrow aspirate and biopsy - (May be performed during screening evaluation) must be done within 30 days prior to treatment initiation.
 - Morphology, flow cytometry, cytogenetics, and molecular tests, and research collection (See Section **5.1**)
- Next Generation Sequencing- panel of myeloid genes from the peripheral blood and/or marrow. (May be performed during screening evaluation) must be done within 30 days prior to treatment initiation.
- Peripheral blood flow cytometry (if peripheral blood blasts present, will trend at end of each treatment cycle until clearance)

To be performed within 24 hours prior to initiating study treatment:

- Serum beta-HCG for females of childbearing potential (FCBP): A female of childbearing potential is a sexually mature woman who:
 - Has not undergone a hysterectomy, tubal ligation, or bilateral oophorectomy
 - Has not been naturally postmenopausal for at least 24 consecutive months (i.e., has had menses at any time in the preceding 24 consecutive months).

In addition, male and female participants should be willing to practice effective birth control prior to study entry, during the study, and for six months following the last study treatment, unless they have had a prior vasectomy, hysterectomy, or bilateral oophorectomy.

An extension up to 72 hours prior to the start of study treatment is permissible in situations where results cannot be obtained within the standard 24-hour window.

3 STUDY IMPLEMENTATION

3.1 STUDY DESIGN

This study consists of two phases:

- Phase I: determination of OBD of BMS-986253 with and without DNMTi for HR- and LR-MDS cohorts, respectively, and
- Phase II: examining the efficacy of BMS-986253 with and without DNMTi for HR- and LR-MDS cohorts, respectively

In the Phase I, subjects will be enrolled to start treatment with BMS-986253 after a minimum of 2 cycles and up to initiation of an 8th cycle of DNMTi.

The safety endpoint will be DLT on D28. In addition, follow up for safety will be assessed 100 days after the last dose of treatment.

OBD will be the lowest tolerated dose level showing optimal biological activity, defined as maximal suppression of serum free IL-8 levels.

Participants enrolled on phase I will be treated at the corresponding BMS-986253 dose level until occurrence of disease progression, death, or unacceptable toxicity or until response assessment on C7D1 (maximum 6 cycles) if no evidence of clinical response. The participants will be followed up for overall, event- and progression-free survival until the study closure. The study will be closed when all enrolled participants have been followed up for at least 8 years or have died.

[figure not shown]
Both Phase I and II portions of study will enroll two cohorts:

A) HR-MDS: subjects with higher-risk MDS that will be treated with BMS-986253 in combination with DNMTi.

B) LR-MDS: subjects with lower-risk MDS that will be treated with BMS-986253 given as monotherapy.

In the Phase II portion, the treatment naïve subjects (or up to 4 cycles of prior DNMTi) will start treatment with BMS-986253 from the first cycle and the efficacy will be assessed until any off-treatment criteria are met (Section 3.8). BMS-986253 will be administered on days 1 and 15 of each cycle, and participants will remain on therapy until disease progression, death, or unacceptable toxicity or taken off therapy if no evidence of clinical response after 6 cycles (C7D1). The participants will be followed up for overall, event- and progression-free survival until the study closure. The study will be closed when all enrolled participants have been followed up for at least 5 years or have died.

Study treatment schema

**In the HR-MDS Cohort, DNMTi therapy (marked by the orange line) may start prior to study enrollment. As stated in the eligibility sections (see Section 2.1.1): For HR-MDS cohort, participants are eligible if they have received a minimum of 2 cycles of DNMTi therapy and up to a maximum of 8 prior cycles for phase I, and up to maximum 4 cycles of DNMTi therapy for phase II.

◊Once enrolled on study, DNMTi administration will be aligned to start on D2 of the on-protocol treatment cycles with oral decitabine and cedazuridine, to be taken once daily for 5 total days (D2-6).

*EOT will occur at disease progression, death, unacceptable toxicity OR if no clinical response is seen by completion of 6 cycles of therapy.

3.1.1 Dose Limiting Toxicity (DLT)

DLT is defined as any of the following:

- Any grade ≥ 3 non-hematologic toxicity that is possibly, probably, or definitely related to study drug, except transient (≤ 48 hour) grade 3 fatigue, nausea, local reactions, flu-like symptoms, fever, headache, infusion reactions, or laboratory abnormalities that are not associated with organ pathology.
- In the absence of active MDS, hematologic DLTs for each arm include:
 - LR-MDS arm: any grade ≥ 4 decrease in ANC or PLTs lasting more than 7 days.
 - HR-MDS arm: any grade ≥ 4 decrease ANC or PLTs lasting more than 28 days.
 - If the bone marrow at the end of cycle 1 of therapy is hypoplastic ($< 5\%$ cellularity), adjustments to treatment schedule will be allowed to delay next cycle for up to 2 weeks after count recovery or if toxicity resolves to Grade 2 or below.
- Liver Injury (DILI) as defined by a positive Hy's Law (<https://www.fda.gov/media/116737/download>):
 - AT (ALT or AST) elevation > 3 times upper limit of normal (ULN), AND
 - Total bilirubin > 2 times ULN, without initial findings of cholestasis (elevated serum alkaline phosphatase), AND
 - No other immediately apparent possible causes of AT elevation and hyperbilirubinemia, including, but not limited to, viral hepatitis, pre-existing chronic or acute liver disease, or the administration of other drug(s) known to be hepatotoxic.
- The following toxicities are not considered dose-limiting in MDS participants:
 - Grade 3 or 4 febrile neutropenia
 - Grade 3 or 4 infection only if a direct complication of cytopenias due to active underlying MDS
 - Grade 3 or 4 hypotension explained by sepsis
 - Grade 3 or 4 hemorrhage/bleeding
 - Other expected direct complication of cytopenia due to active myeloid malignancy
- Any adverse reaction that leads to dose reduction or withdrawal.

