2 ELIGIBILITY ASSESSMENT AND ENROLLMENT

2.1 ELIGIBILITY CRITERIA

2.1.1 Inclusion Criteria

1. Participants must have histologically or cytologically confirmed MDS according to 2016 WHO criteria[1]
 - a. And:
2. have HR-MDS (R-IPSS ≥ 3.5) and received a minimum of 2 and maximum of 8 prior cycles for phase I and 4 for phase II of DNMTi therapy, or
3. have LR-MDS (R-IPSS <3.5),
 - a. and, at least one cytopenia:
 - i. granulocytes $< 1.0 \times 10^9/L$ and/or
 - ii. hemoglobin $< 110 \text{ g/L}$ with signs/symptoms of symptomatic anemia or transfusion-dependency
 - iii. platelets $< 100 \times 10^9/L$

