3.1.2 Dose Escalation

Participants will receive BMS-986253 A safety lead-in will be performed. The safety lead-in will be 28 days in length and consist of 2 doses of BMS-986253 (on days 1 and 15) with a safety evaluation through day 28. Dose escalation will proceed in cohorts of 3–6 participants. The MTD is the dose level at which no more than 1 of up to 6 participants experience DLT during one cycle (28 days) of treatment, and the dose below that at which at least 2 (of ≤ 6) participants have DLT as a result of the drug. If a participant did not experience DLT and did not finish treatment, he or she will not be evaluable for toxicity and will be replaced in the dose level. Participants will be taken off treatment if unacceptable toxicity occurs and is attributed to all therapeutic

agents (see section 3.8). These patients will also be evaluated for safety and efficacy (see Section 7.4.1 and 8).

Dose Escalation Schedule	
Dose Level	Dose of BMS-986253
Level -1	600 mg IV Q2W over 60 minutes
Level 1	1200 mg IV Q2W over 60 minutes ^a
Level 2	2400 mg IV Q2W over 120 minutes ^b
Level 3	3600 mg IV Q2W over 120 minutes ^b

^a 60 minute duration will be used for pts weighing > 35 kg. For pts weighing < 35 kg the infusion duration should be 120 minutes.

^b 120 minute duration will be used for pts weighing > 35 kg. For pts weighing < 35 kg the infusion duration should be 180 minutes.

Dose escalation will follow the rules outlined in the Table below.

Number of Participants with DLT at a Given Dose Level	Escalation Decision Rule
0 out of 3	Enter up to 3 participants at the next dose level
≥ 2	Dose escalation will be stopped. This dose level will be declared the maximally administered dose (highest dose administered). Up to 3 additional participants will be entered at the next lowest dose level if only 3 participants were treated previously at that dose.
1 out of 3	Enter up to 3 more participants at this dose level. 
 • If 0 of these 3 participants experience DLT, proceed to the next dose level. • If 1 or more of this group develop DLT, then dose escalation is stopped, and this dose is declared the maximally administered dose. Up to 3 additional participants will be entered at the next lowest dose level if only 3 participants were treated previously at that dose.

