3.3 DOSE MODIFICATIONS

No dose modifications are allowed for BMS-986253. Dose modifications for toxicity related to the DNMTi used will be done according to standard of care per the FDA product label recommendations.

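### Read literally, the condition on hematologic DLTs in section 3.1.1 switches off the LR-MDS criterion in cycle 1; the likely effect is small and a short rewording cures it

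*Combined protocol and SAP*

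**What the plan says.** Section 3.1.1 makes the hematologic criteria for both arms conditional: "In the absence of active MDS, hematologic DLTs for each arm include". For LR-MDS the criterion that follows is a grade 4 or worse "decrease in ANC or PLTs lasting more than 7 days". Active MDS is not defined in section 3.1.1, the response criteria (6.3.1), the abbreviations or the appendices.

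Section 2.1.1 requires confirmed MDS of every participant and adds for LR-MDS "and, at least one cytopenia": granulocytes below 1.0, platelets below 100, or hemoglobin below 110 g/L with symptoms or transfusion dependency. Section 3.1.2 sets the DLT period at one 28-day cycle.

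Other lines bear on attribution:

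- Non-hematologic toxicity counts when "possibly, probably, or definitely related to study drug".
- Among events that are not dose-limiting, section 3.1.1 lists "Grade 3 or 4 infection only if a direct complication of cytopenias due to active underlying MDS".
- The MTD sentence in section 3.1.2 refers to a level at which at least two "participants have DLT as a result of the drug".
- The last DLT line is "Any adverse reaction that leads to dose reduction or withdrawal", while section 3.3 states "No dose modifications are allowed for BMS-986253".

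**The concern.** A DLT criterion for a 28-day window has to be one that an enrolled participant can meet within that window. Here the condition is a disease state that every LR entrant has. If it is applied as written, a prolonged grade 4 fall caused by BMS-986253 in a participant who continues treatment is not a DLT.

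DLT counts decide each 3+3 step: with three participants at a level, one event means expanding to six and two mean stopping. They also feed the section 10.4.4 monitor, which tracks the probability of DLT against 0.2. The LR arm is monotherapy, so it is the arm in which such a fall can most clearly be ascribed to the antibody.

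A second gap lies beside the first. The word decrease has no pre-dose reference. Section 2.1.2 excludes ANC below 100 only together with frequent infection hospitalizations, and low platelets only when transfusion-refractory or with ongoing or uncontrolled hemorrhage. Some participants can therefore enter with very low counts, and the text does not say how that lineage is scored.

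**Working it through.** **1. Can an LR participant be free of active MDS within the window?** The LR entry cut-offs (granulocytes <1.0, hemoglobin <110 g/L, platelets <100) mirror the blood thresholds for complete remission in section 6.3.1 (neutrophils ≥1.0, hemoglobin ≥11 g/dL, platelets ≥100). An LR entrant therefore does not meet complete remission at baseline. Responses must last at least 4 weeks, so a remission beginning on study could not ordinarily be confirmed inside 28 days. Taken literally, the condition is not met in cycle 1.

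**2. Is there another route to a DLT?** Yes, the last DLT line. BMS-986253 dose changes are not allowed, so in monotherapy that route means withdrawal. An affected participant who stays on drug is not caught.

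**3. The plan's own figure.** With a Beta(1,1) prior, the section 10.4.4 boundary is the smallest x with Pr(p > 0.2 | Beta(1+x, 1+n−x)) > 0.80, from n = 6. This gives 2/6, 3/7, 4/11, 5/15, 6/20, 7/24, 8/28 and 9/32, exactly as printed (for example, posterior 0.852 at 2/6). The arithmetic is sound; what is unclear is which events enter the count.

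**4. What event rate is plausible?** The documents give no rate of drug-caused grade 4 falls lasting more than 7 days in MDS, so I assume a range from solid-tumor data.

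- With nivolumab there were no DLTs among 144 participants (section 1.2.4.1).
- Section 14.1.2 lists related events above 2% in those 144. The smallest listed count is 3 (3/144 = 2.08%). Neither neutropenia nor thrombocytopenia is listed, so each had at most 2/144 (1.4%), or 4/144 (2.8%) together if nobody had both and each was reported under one term.
- One-sided 95% Clopper-Pearson upper limits are 2.1% for 0/144 (assuming all were DLT-evaluable), 4.3% for 2/144 and 6.2% for 4/144.

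These rates treat every reported case, whatever its grade or duration, as a qualifying event.

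**5. Effect on decisions.** With no other DLTs, the chance that the 3+3 escalates past a level is (1−p)³ + 3p(1−p)⁵. At p = 2/144 this is 0.9589 + 0.0389 = 0.9978. At p = 4/144 it is 0.9190 + 0.0724 = 0.9913. The pause probability is the exact chance that the running count reaches the step 3 boundary at any n from 6 to 25, where 25 is the LR enrollment goal.

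| Assumed rate p | 3+3 escalates, events counted | Escalates, not counted | Pause within 25, events counted |
|---|---|---|---|
| 1.4% (2/144) | 99.8% | 100% | 0.3% |
| 2.1% (upper limit, 0/144) | 99.5% | 100% | 0.6% |
| 2.8% (4/144) | 99.1% | 100% | 1.2% |
| 4.3% (upper limit, 2/144) | 98.0% | 100% | 2.8% |
| 6.2% (upper limit, 4/144) | 96.0% | 100% | 5.9% |
| 10% (illustration) | 90.6% | 100% | 15.2% |

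Uncounted, these events add nothing to the pause probability, though other toxicities can still trigger a pause.

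**6. Allowing for withdrawals.** If half of the affected participants are withdrawn and so count anyway, the literal reading works at p/2. It then escalates 99.5% at 4.3% and 98.9% at 6.2%, so the gap between readings shrinks to about 1.5 points (99.5 − 98.0) and 2.9 points (98.9 − 96.0).

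**The case against.** The strongest reply is that the literal reading empties a deliberate clause. The authors gave LR-MDS its own 7-day threshold, against 28 days for HR-MDS, and would not have done so for a criterion that never applies. The infection line in the same section speaks of cytopenias due to underlying MDS, and the MTD sentence requires that the DLT result from the drug. Both point to the sense of not due to MDS. Sections 8.1.5 and 8.2 also require an investigator to classify each adverse event as related or not, with an alternate cause if not, and section 3.1.2 requires a sponsor report setting out the criteria met before the next dose level.

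Most of this stands as evidence of intent, and I accept that attribution was probably meant. It does not change the rule as written. Where section 3.1.1 wants attribution to the drug it says so, for non-hematologic toxicity, and the hematologic lines have no such words. The MTD sentence only narrows events that already qualify as DLTs. Recording relatedness and reporting to the sponsor make an event visible without saying whether it counts.

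A reader might infer that drug-caused marrow toxicity in the LR arm would go unnoticed, or that the phase II dose is likely to be wrong. The documents support neither. Withdrawals count, weekly team review and event recording continue, and the rates that the documents suggest barely move the 3+3.

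**Conclusion.** The point holds as a drafting fault in a safety rule. Followed to the letter, the LR hematologic criterion cannot operate in the window it was written for, and a drug-caused event in a participant who stays on drug is missed by both the 3+3 and the section 10.4.4 monitor. The severity is minor.

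At 2/144 to 4/144 the difference in escalation is under one percentage point, and at the 6.2% upper limit it is four points. It becomes material only at about 10%. The documents do not suggest such a rate: in the 15-participant monotherapy study no DLT was reached and all related events were grade 1 or 2 (section 1.2.4.1). They cannot exclude it either, since the one-sided 95% upper limit for 0/15 is 1 − 0.05^(1/15) = 18.1%, and none of these participants had marrow already compromised by MDS. The figures rest on solid-tumor rates carried over to MDS, no other DLTs and, in the uncounted column, no withdrawals.

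The conclusion is for the LR arm only. It is tempting to extend it to HR-MDS, but phase I HR participants have had 2 to 8 DNMTi cycles and Appendix F allows complete response as disease status at enrollment, so some could lack active disease.

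**What to change.** For the LR arm, replace the condition in section 3.1.1 with wording such as:

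*A new grade 4 ANC or platelet count lasting more than 7 days, in a lineage that was below grade 4 before the first dose, unless attributed to underlying MDS on evidence other than the fall in counts itself (for example, increased marrow or blood blasts). A lineage already at grade 4 at baseline is not assessed for this criterion.*

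The requirement for independent evidence matters. Section 6.3.1 includes worsening cytopenias, count decrements and transfusion dependence among its failure and progression criteria, so a plain exemption for disease progression could let a drug-caused fall excuse itself.

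The cost is two or three sentences. No new assessment and no change in sample size is needed: the baseline CBC (section 2.4), the weekly cycle 1 CBCs in both phases and the phase I marrow at C1D28 (section 3.4) are already scheduled, and in phase II a marrow is already called for with aplasia or suspected progression. The downside is that a few disease-related falls in participants starting near grade 4 may be counted as DLTs. The grade and duration thresholds remain the clinical team's choice.
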